#### 8.5 Electronic Diary and Activity Monitoring Sub-Study Endpoints

For patients participating in the sub-study, the electronic patient reported outcome data and actigraphy data collected from the activity monitor will be obtained by Edwards GHER department outside of the electronic data capture (EDC) RAVE system. These data will be analyzed by summary statistics for the AT population, and more in-depth analyses will be performed and reported by GHER separately.

### 8.6 Exploratory Computed Tomography (CT) Endpoints

The following data will be assessed and summarized descriptively at 30 days and 12 months (when the data are available).

- Cardiac remodeling (e.g., RV dimensions and volume)
- EVOQUE frame dimensions
- EVOQUE leaflet assessment
- EVOQUE positioning

#### 8.7 Patient-centered Exploratory Endpoints

The patient-centered exploratory endpoints (as described in Section 3.7) will be analyzed as categorical variables and counts and percentages in the AT population.

- Exploratory Device Success (30 days and all post-procedural intervals)
- Exploratory Procedural Success (30 days)
- Exploratory Technical Success (at exit from OR/Cath lab)
- Exploratory Individual Patient Success (1 year)

The patient-centered exploratory endpoints (as described in Section 3.7) will be analyzed as categorical variables and counts and percentages in the AT population.

## 9. ANALYSIS OF SAFETY

#### 9.1 Deaths

The primary cause of death will be summarized descriptively by counts and percentages at 30 days and 1 year and annually thereafter.

#### 9.2 Adverse Events

All Clinical Events Committee (CEC)-adjudicated and site-reported AEs with onset on or after the procedure date (Day 0) after implant will be summarized by early events ( $\leq$  30 days) and late events (> 30 days) for the Enrolled Population. Summaries of incidence rates (counts and percentages) will be reported. SAEs will be summarized by early events ( $\leq$  30 days) and late events ( $\geq$  30 days) as well.

Edwards	Revision Date: August 1, 2022		Rev		For Use Only by Affiliates of Edwards Lifesciences	Page 17 of 18	
	Title	Statistical Analysis Plan for TRISCEND Study (2019-06)					

AEs with onset prior to procedure will not be collected. Listings for all AEs and SAEs that occur post-procedure in the Enrolled Population will be provided.

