8.5.3. Enrolled Patients

A patient will be considered “enrolled” at the time of skin incision to introduce the EVOQUE System into the body. Enrolled patients will be assigned a unique identification number by the study Sponsor. The patient ID number together with the patient initials shall be used to identify the patient on all study-related documents.

A study procedure should be scheduled within 90 days of a patient signing an informed consent.

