10.4. Quality Control and Quality Assurance Procedures

Because of the potential for errors and inaccuracies in entering data into eCRFs, originals or photocopies of all relevant procedural records and reports, post-procedural examinations, laboratory and other test results may be kept on file in the Investigator's patient study files. Access to eCRFs and copies of test results must be available at all times for inspection by the study monitor.

All clinical sites will be audited periodically by a study monitor employed or contracted by the Sponsor for protocol adherence, accuracy of eCRFs, and compliance to applicable regulations. Evident patterns of non-compliance with respect to these standards will be cause for the site to be put on probation for a period of one month. If corrective actions are not subsequently undertaken, the clinical site will be asked to withdraw.

The Sponsor will provide data management through a secure, password protected EDC system accessible via the Internet. Passwords will be issued to appropriate data management personnel to ensure confidentiality and protection of the data by allowing variable levels of access to the computer system.

11. Adverse Event Reporting and Assessments

Adverse events will be captured for all study patients from the time of enrollment until the patient's participation has ended (i.e., completion of study, lost to follow-up, withdrawal of consent, or patient has died).

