#### **ANALYSIS POPULATIONS** 4.

Analysis will be performed for the Enrolled, As-Treated (AT), and Per-Protocol (PP) populations defined below:

- Enrolled Population: All patients enrolled in the study, defined as patients who sign informed consent and have had the study procedure attempted (attempted defined as skin incision for study device). Enrolled population will be used for the safety analyses.
- As-Treated Population: A subset of the enrolled population who have had the study device implanted at • the exit of procedure room. The AT population will be the analysis population for performance and functional endpoint analysis.
- Per-Protocol Population: A subset of the AT population who had no protocol deviations relating to • inclusion and exclusion criteria for the trial.

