#### DEFINITIONS 5.

#### 5.1 Analysis Dates and Days

Reference Start Date and Day 0

The reference start date is defined to be the date of the index procedure. The index procedure is defined as the time the first skin incision for the study device is established. If a patient has multiple procedure forms, information will be presented on the procedure with the first date when the site has indicated that the interventional skin incision for study device is performed. If no form has this indicated, then the procedure information corresponding to the date of the first procedure will be used.

The reference start date is considered to be day 0.

Last Participation Date

The Last Participation Date is defined as the last date the patient was seen (refer to the programming convention for complete details).

Last Participation Day

Last Participation Day = Last Participation Date – Reference Start Date

Note: Last Participation Day is used as censor day for Kaplan-Meier analysis.

	Revision Date: August 1, 2022		Rev		For Use Only by Affiliates of Edwards Lifesciences	Page 12 of 18
Edwards	Title	Statistical Analysis P	lan foi	 TRIS	CEND Study	r (2019-06)

• Study Day

Study Day = Date – Reference Start Date

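### The after-implant condition in the SAP 9.2 adverse event summary contradicts the incision-based Enrolled population and, read literally, removes every event in patients who were never implanted

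*SAP*

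**What the plan says.** SAP 9.2 covers CEC-adjudicated and site-reported events "with onset on or after the procedure date (Day 0) after implant will be summarized by early events" (30 days or less) and late events, for the Enrolled population. SAEs are to be summarised in the same way. The section adds that "AEs with onset prior to procedure will not be collected" and that "Listings for all AEs and SAEs that occur post-procedure in the Enrolled Population will be provided".

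The population and time origin are defined elsewhere:

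- SAP 4: Enrolled patients are those who have consented and who "have had the study procedure attempted (attempted defined as skin incision for study device). Enrolled population will be used for the safety analyses". Implantation is a condition only for the As-Treated population, "A subset of the enrolled population who have had the study device implanted at" exit from the procedure room.
- SAP 5.1: Day 0 is the date of the index procedure, and "The index procedure is defined as the time the first skin incision for the study device is established".
- Protocol 11, opening paragraph: "Adverse events will be captured for all study patients from the time of enrollment". Protocol 8.5.3 places enrolment "at the time of skin incision to introduce the EVOQUE System into the body".

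**The concern.** The sentence in SAP 9.2 sets two onset conditions that do not match. The first, on or after Day 0, is anchored to incision. The second, *after implant*, is anchored to a later event that some Enrolled patients never reach. A patient whose procedure is aborted has no implant date, so no event in that patient can satisfy the second condition.

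Protocol 8.6 expects such patients and follows them specifically for safety. Their events bear directly on procedural risk, which a device feasibility study sets out to describe. If the sentence were programmed literally, these patients would count in the Enrolled population and contribute no events to the AE or SAE summary. The tables could also disagree: a major access-site complication in an aborted case could count as an MAE under SAP 8.1 and be missing from the SAE summary under SAP 9.2.

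A programmer might not recognise the phrase as a slip, because an implant restriction on safety appears elsewhere. Protocol 12.2 assigns safety to the enrolled population, while Protocol 12.4 analyses MAEs in the implanted population.

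**Working it through.** The plan states no figure on this point, so there is nothing to reproduce. The check compares the provisions and then bounds the effect.

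**1. Provisions compared**

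| Place | Anchor or scope | Implant required? |
|---|---|---|
| SAP 4, Enrolled | Consent and skin incision | No |
| SAP 5.1, Day 0 | Date of first skin incision | No |
| Protocol 8.5.3 and 11, AE capture | From enrolment, i.e. incision | No |
| Protocol Table 9 | AE assessment during the index procedure | No |
| Protocol 8.6 | Safety follow-up of attempted-but-not-implanted patients | No |
| Protocol 12.5 | Early and late summary of all AEs | No |
| SAP 6.2, partial onset dates | Earliest possible date on or after the index procedure | No |
| SAP 8.1, 30-day MAE | Enrolled and As-Treated | No, in Enrolled |
| SAP 3.4.3, listing | All AEs and SAEs, Enrolled | No |
| SAP 9.2, AE/SAE summary | On or after Day 0 and after implant | **Yes** |

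SAP 9.2 is the exception. SAP 10 declares only the exploratory endpoints as a departure from the protocol, so no narrowing of AE scope is announced.

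**2. Who is lost under a literal reading**

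- *Never implanted:* all events, because there is no implant date.
- *Implanted, onset between incision and implant:* this depends on the precision of the onset data. SAP 5.1 computes study day as a difference of dates, and the minimum AE report in Protocol 11.2 asks for the date of the event. With dates alone, an event before valve release shares the implant date and would probably be kept. It is lost only if clock times are compared.

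**3. Bound for the never-implanted patients**

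Let N = 200 (the planned maximum, SAP 2.3), k = number never implanted, p = proportion of implanted patients with a counted AE, and q = proportion of never-implanted patients with an AE. The documents give no k, p or q, so all three are assumptions.

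- All events counted: [(N − k)p + kq] / N
- Literal filter, denominator N: (N − k)p / N
- Shortfall: kq / N, which does not depend on p and is at most k / N

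| k (share of 200) | Shortfall, q = 1 | Shortfall, q = 0.5 |
|---|---|---|
| 2 (1%) | 1.0 point | 0.5 point |
| 5 (2.5%) | 2.5 points | 1.25 points |
| 10 (5%) | 5.0 points | 2.5 points |
| 20 (10%) | 10.0 points | 5.0 points |

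Example with k = 10, p = 0.25, q = 0.5: all events (190 × 0.25 + 10 × 0.5)/200 = 26.25%; literal filter 190 × 0.25/200 = 23.75%; shortfall 2.5 points.

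**4. Effect of the SAP 6.1 denominator rule**

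SAP 6.1 counts patients who had the event or were followed to the upper bound of the visit window, which for the 30-day visit is 30 + 7 = 37 days. If that rule governs this table, a never-implanted patient who exits at 30 days could leave the denominator as well. If all k did, the reported value would be p and the shortfall k(q − p)/N, which is no larger than kq/N. The bound of k / N still holds.

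**The case against.** The strongest reply is that *after implant* is a drafting remnant. The same sentence already sets the start at Day 0 and names the Enrolled population, which would make little sense if implantation were required. The only exclusion the section states openly is events before the procedure. On this view the defect is an ambiguity, and a sensible programmer would include everything from incision onward. This may well be right about intent. It does not remove the need to correct the text, because SAP 1 presents the document as detailed instructions for each analysis, and the literal instruction is wrong for never-implanted patients.

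Three further parts of the reply stand and limit the point.

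- A reader might infer that all complications between incision and valve release will disappear. The documents do not support that. The timing conventions shown are by date. Table 9 does record the timing of implant procedures, but nothing visible provides an AE onset time to compare with it.
- A reader might infer that the study as a whole will understate procedural harm. It would not follow. The Enrolled MAE analysis in SAP 8.1 includes severe bleeding, major access-site and vascular complications and major cardiac structural complications without an implant condition, and SAP 3.4.3 promises a listing of all AEs and SAEs in the Enrolled population.
- The term *post-procedure* in the SAP 9.2 listing sentence is not clearly a third starting point. It follows directly on, and contrasts with, the sentence about events before the procedure, and Protocol 12.5 uses the same term as the ordinary origin for early and late events.

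**Conclusion.** The contradiction is real and lies in a stated analysis rule. SAP 9.2 adds an implant condition that conflicts with the Enrolled definition, Day 0, the start of AE capture and the Protocol 12.5 summary. Read literally, it removes all events in attempted-but-not-implanted patients from the AE and SAE counts. It does not show that events will in fact be dropped.

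The reach is limited to the descriptive AE and SAE summaries in SAP 9.2; the safety endpoint is untouched. On an assumed non-implant rate of 1% to 10% of 200 patients, the any-AE percentage would fall by at most 1 to 10 points, and by 0.5 to 5 points if half of those patients had an event and the denominator stayed at 200. Those rates are illustrative. Any loss of pre-implant events in implanted patients would come on top, arises only if onset times are used, and cannot be sized from the documents. The wording should be corrected before the tables are programmed.

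**What to change.** In SAP 9.2, delete *after implant* and define inclusion as onset on or after skin incision for the study device (Day 0), for all Enrolled patients whether or not implanted. State that the SAE summary uses the same rule. Optionally, replace *post-procedure* in the listing sentence with the same wording so that it matches SAP 3.4.3.

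The cost is one or two wording edits. The protocol already captures events from incision and follows never-implanted patients for safety, so no new data are needed, and the change restores the scope of Protocol 11 and 12.5.

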8.6. Study Exit Criteria and Procedures

All patients that sign an informed consent document for this study will have the study exit reason documented in the medical record and on the appropriate eCRF. Patients may exit the study for any of the following reasons:

- **Screen Failure:** Patients who are consented to participate in the study, but do not fulfill enrollment criteria.

- **Study Device Attempted but Not Implanted:** Enrolled patient for whom the implant procedure was prematurely aborted will be followed either for 30 days (for only safety evaluations) OR until resolution, stabilization, or is adequate explanation of any implant-related AEs and then exited from the study. Examples include:
 - Procedure attempted (i.e. skin incision to introduce the EVOQUE System) but patient did not receive a study device
- **Study Device Re-intervention/Explant:** Patient who has a surgical re-intervention for study device explant will be followed for 30 days after the re-intervention for safety evaluations only or until resolution of any AEs related to the re-intervention and then exited from the study. Note: a patient who has a percutaneous re-intervention where the study device remains in place will continue to be followed for the duration of the study.
- **Withdrawal**
 - **Patient Withdrawal:** A patient may voluntarily withdraw from the clinical study at any time, without penalty or loss of benefits to which they are otherwise entitled.
 - **Physician Withdrawal:** An Investigator also has the right to withdraw a patient if s/he feels it is in the best interest of the patient to do so.
- **Patient death**
- **Lost to Follow-up**
 - If a patient cannot be reached for a follow-up visit, the Investigator will document contact efforts and/or efforts to obtain hospital records in the appropriate eCRF. If a patient cannot be reached in any way, or misses a visit, the patient will be considered “unable to contact” for that time interval.
 - After 3 documented unsuccessful attempts to make contact, a certified letter will be sent to the patient’s residence. If there is no response after a certified letter is sent, the patient will be classified as “lost to follow-up”.
- **Completion Per Protocol**

Withdrawn patients will not have any study follow-up visits or procedures after the time of study exit. All data collected up until the time of withdrawal, including imaging studies such as echocardiography scans, will be analyzed.

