12.3. General Approach

For continuous variables, results will be summarized with the number of observations, mean, standard deviation, median, minimum, maximum, and 90% confidence interval (CI) by normal approximation. For categorical variables, results will be summarized with patient count, percentage, and 90% CI by normal approximation, where appropriate.

Survival analysis techniques will be used to analyze time-to-event variables. Patients without events will be censored at their participation date in the study. For patients who did not have an event but remain in the study, they will be censored at the database extract date. Time to first event curves will be constructed using Kaplan-Meier estimates.

Descriptive statistics will be presented at each assessment, including change from baseline to subsequent time point for selected endpoints. For the determination of event rates, the number of all patients in the patient population will be used as the denominator. For variables ascertained at follow-up visit, the denominator will be based on number of evaluable patients. Unless otherwise noted, patients with missing data will be excluded from the denominator.

When the sample size is small (e.g., <10 patients), analysis may be performed in the form of listings only.

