12.5. Additional Safety Analysis

A summary of the percentage of patients who experience an early adverse event (\leq 30-day post-procedure) and late adverse event ($>$ 30 days post-procedure) will be reported for all adverse events.

The count and percentage of patients who experience newly identified ECG changes, as identified by ambulatory cardiac monitoring, resulting in PPM, ICD, or CRT device implantation will be reported. Two-sided 90% confidence intervals will be constructed around the percentage of patients who experience newly identified ECG changes resulting in PPM, ICD, or CRT device implantation. This

analysis will only include patients who undergo ambulatory cardiac monitoring. The reported confidence intervals will be compared to the range as reported in the literature data.

The count and percentage of patients who have a change in therapy (either new pacemaker for bradycardia or new ICD/new pharmacotherapy for tachycardias) as a result of ECG changes identified by ambulatory cardiac monitoring will be reported. This analysis will only include patients who undergo ambulatory cardiac monitoring.

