### 6. DATA AND ANALYSIS CONVENTIONS

#### 6.1 General Conventions

For continuous variables, results will be summarized with the number of observations, mean, standard deviation, median, minimum, maximum, and 90% confidence interval (CI) by normal approximation. For categorical variables, results will be summarized with patient count, percentage, and 90% CI by normal approximation, where appropriate.

Survival analysis techniques will be used to analyze time-to-event variables. Patients without events will be censored at their last participation date in the study. For patients who did not have an event but remain in the study, they will be censored at the database extract date. Time to first event curves will be constructed using Kaplan-Meier estimates. Descriptive statistics will be presented at each assessment, including change from baseline to subsequent time point for selected endpoints. For the determination of event rates, the number of patients in the patient population who have had the events or have been followed up to the upper bound of the follow-up visit window will be used as the denominator. Unless otherwise noted, patients with missing data will be excluded from the denominator.

When the sample size is small (e.g., <10 patients), analysis may be performed in the form of listings only.

Quality of life questionnaires will be scored according to algorithms provided by the vendor. The various summary scores produced by the algorithms will be analyzed as continuous variables.

Unless otherwise specified, confidence limits will be two sided, using alpha = 0.05.

Unless otherwise specified, the precise form of each algorithm will be the default of SAS, using the latest release installed at Edwards Lifesciences (Edwards) at the time of analysis.

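### The late adverse event tables give a crude percentage over an open-ended period, with no time at risk and a denominator on which protocol and SAP disagree

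*SAP*

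**What the plan says.** SAP 9.2 divides CEC-adjudicated and site-reported AEs into early events (up to day 30) and "late events (> 30 days) for the Enrolled Population". On the statistic it says "Summaries of incidence rates (counts and percentages) will be reported". The next sentence begins "SAEs will be summarized by early events" and, as printed, sets early at 30 days or fewer and late at 30 days or more. Protocol 12.5 plans the same kind of table: "A summary of the percentage of patients who experience an early adverse event", and likewise for late events. Neither section gives the late period an end, a fixed time point or a person-time measure.

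Two general rules could supply the denominator:

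- Protocol 12.3, for event rates: "the number of all patients in the patient population will be used as the denominator".
- SAP 6.1, for event rates: the number of patients who "have had the events or have been followed up to the upper bound of the follow-up visit window will be used as the denominator".

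SAP section 10, which lists changes from the protocol's analyses, names only the patient-centered exploratory endpoints.

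Follow-up will differ between patients. Protocol 6.3 expects 18 to 24 months of enrollment and then 5 years of follow-up. Under Protocol 8.6, a patient in whom implantation was attempted but not completed "will be followed either for 30 days (for only safety evaluations) OR until resolution" of implant-related events, and then leaves the study. Protocol 11.7 has AE summaries going to FDA every year.

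Kaplan-Meier estimates to 5 years are planned for the components of the major adverse event (MAE) composite (SAP 8.1) and for all-cause mortality, heart failure hospitalization and non-elective re-intervention (SAP 8.4).

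**The concern.** A percentage of patients is a fair summary of the first 30 days, when nearly everyone is observed for the same short time. The late period can run from a few days to almost 5 years per patient. A late percentage with no time attached mixes those lengths, and although SAP 9.2 calls it an incidence rate, it has no time in its denominator. Two annual reports from the same device with the same underlying risk would show different late percentages.

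The denominator adds a second problem. Protocol 12.3 keeps patients who died or left early and so had little or no chance of a recorded late event. SAP 6.1, read literally, drops every event-free patient who did not reach the end of the window but keeps anyone with an event. The first rule pulls the figure down and the second pushes it up. Because the late period has no visit window, SAP 6.1 cannot be applied without a further definition, so two programmers could follow the plan and report different numbers.

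At stake are events outside the Kaplan-Meier lists, such as valve thrombosis, endocarditis and hemolysis. Guidance for future study designs is a stated objective, and a late percentage without exposure is a weak basis for it.

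**Working it through.** The documents state no late AE rate, so there is no figure to reproduce. What follows is an illustration.

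**Assumptions (none from the documents).** After day 30 the AE hazard is λ and the exit hazard (death or withdrawal) is μ, both constant per year. A share q of enrolled patients has gone by day 30. Central case: λ = 0.10, μ = 0.10, q = 5%. Range: λ 0.05 to 0.20, μ 0.05 to 0.15, q 5% to 10%. Late time available with T years of follow-up is L = T − 30/365.

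**Formulas.**

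- Chance of an observed late event for a patient present at day 30: p = λ/(λ+μ) × (1 − exp(−(λ+μ)L))
- Protocol 12.3, all enrolled: (1 − q) × p
- SAP 6.1, taking T as the end of the window: p / (p + exp(−(λ+μ)L))
- Kaplan-Meier from day 30: 1 − exp(−λL)

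**Central case at T = 5.** L = 4.918 and exp(−0.984) = 0.374.

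- p = 0.5 × (1 − 0.374) = 0.313
- All enrolled: 0.95 × 0.313 = 29.7%
- SAP 6.1: 0.313 / (0.313 + 0.374) = 45.6%
- Kaplan-Meier: 1 − exp(−0.492) = 38.8%

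| Follow-up | All enrolled | Present at day 30 (p) | Kaplan-Meier | SAP 6.1 |
|---|---|---|---|---|
| 1 year | 8.0% | 8.4% | 8.8% | 9.2% |
| 2 years | 15.1% | 15.9% | 17.5% | 18.9% |
| 5 years | 29.7% | 31.3% | 38.8% | 45.6% |

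If the exits are deaths treated as a competing event, p is the cumulative incidence. The protocol rule lies below both p and Kaplan-Meier, and the SAP rule lies above both, so they err in opposite directions whichever reference is preferred.

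**Range.** At 5 years the assumed grid gives 14.1% to 53.8% (all enrolled), 24.1% to 72.4% (SAP 6.1) and 21.8% to 62.6% (Kaplan-Meier). The gap between the two denominator rules runs from 5.6 points (18.5% against 24.1%) to 30.2 points (42.2% against 72.4%).

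**Data cut.** With uniform enrollment over 24 months, λ = 0.10 and no exits, the crude percentage is 8.6%, 17.3%, 32.3% and 38.8% at cuts 2, 3, 5 and 7 years after first enrollment. The risk is the same at each cut.

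**Rate per patient-year.** In the central case, expected late time to first event, exit or end of follow-up is (1 − exp(−(λ+μ)L))/(λ+μ) per patient present at day 30. At 5 years that is 0.626/0.2 = 3.13 years, and 0.313/3.13 = 0.10. At 1 year it is 0.168/0.2 = 0.84 years, and 0.084/0.84 = 0.10. The rate is 10 per 100 patient-years both times.

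**Early leavers alone.** They scale the all-enrolled figure by (1 − q). For q of 2%, 5% or 10%, 196, 190 or 180 of 200 patients remain, a relative reduction of 2% to 10%. That is much smaller than the effect of follow-up length.

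**The case against.** The strongest reply is that any cumulative measure grows with time. Kaplan-Meier itself goes from 8.8% to 38.8% in the table above, so growth alone is not bias. That is correct. The difference is that a Kaplan-Meier value belongs to a stated time and handles unequal follow-up, while the late percentage has no stated time and averages over whatever follow-up exists at the cut.

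The reply also has force on scope. This is a descriptive, single-arm feasibility study whose sample size has no statistical justification (SAP 2.3), and the protocol itself specifies the early and late percentages.

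A reader might infer more than the documents support:

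- *That the figure reflects follow-up rather than risk.* It reflects both.
- *That early leavers stay in the denominator and make the device look safer.* This holds only under Protocol 12.3. SAP 6.1 would drop event-free early leavers and can push the figure above Kaplan-Meier.
- *That patients without an implant cannot have a late event.* Protocol 8.6 allows them to be followed beyond 30 days until implant-related events resolve.
- *That the late percentage is the only summary of other device events.* Full AE and SAE listings are planned. Exploratory device success is reported at each visit to 5 years and covers structural and functional failure, and CT leaflet assessment is planned at 30 days and 12 months. None of these gives an event-specific late rate, but they are not nothing.

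**Conclusion.** The point holds, limited to the general AE and SAE tables. Their late percentage carries no time at risk, and its denominator is not determined because Protocol 12.3 and SAP 6.1 conflict and SAP section 10 does not declare the change. In the central case the choice of rule moves the 5-year figure by 15.9 points (45.6 − 29.7), and follow-up length moves the all-enrolled figure by a factor of 3.7 (29.7 / 8.0). These sizes rest on assumed constant hazards and an assumed early loss. The direction of the two errors is the same at every point of the range tried. Separately, the SAE sentence as printed counts day 30 in both periods.

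This is a cheap improvement to a secondary table. It does not affect the 30-day MAE endpoint or the late outcomes that have Kaplan-Meier estimates.

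**What to change.** In SAP 9.2:

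1. Define the denominator of the late AE and SAE percentages as enrolled patients still in follow-up after day 30. State that this overrides SAP 6.1 and Protocol 12.3 for this table, and list it in SAP section 10.
2. Add the number of events per 100 late patient-years, counting time from day 31 to death, exit or data cut, overall and by year. The late percentage will still grow with follow-up, so it should be read beside this rate.
3. Define late SAEs as more than 30 days, matching the rule already given for AEs.

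The split at day 30 and the early percentages otherwise stay as they are. No new data are needed, because SAP 5.1 already defines the reference start date and the last participation date. The cost is SAP wording and one extra table column. Patient-year rates assume a roughly constant hazard, and the by-year split limits that assumption to within each year.

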## 10. CHANGES FROM PROTOCOL SPECIFIED ANALYSES

The patient-centered exploratory endpoints are not specified in the study protocol and only described in Section 3.7 of this SAP.

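### SAP 9.2 counts an SAE that starts on day 30 as both early and late, which conflicts with its own AE split and with Protocol 12.5

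*SAP*

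**What the plan says.** SAP 9.2 gives two early/late splits in one paragraph.

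- **AEs:** they "will be summarized by early events ( $\leq$ 30 days) and late events (> 30 days) for the Enrolled Population".
- **SAEs:** the sentence that begins "SAEs will be summarized by early events" reads in full "SAEs will be summarized by early events ( $\leq$ 30 days) and late events ( $\geq$ 30 days) as well".

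The early side is the same in both. The late side is strictly after day 30 for AEs, but includes day 30 for SAEs.

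Protocol 12.5 has a single split. Early runs up to and including 30 days, and the percentage of patients with a "late adverse event ($>$ 30 days post-procedure) will be reported for all adverse events". Protocol 11.1.2 defines an SAE as an AE that led to one of the listed serious outcomes, so the protocol's split already covers SAEs.

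SAP 5.1 fixes the day count: "The reference start date is considered to be day 0" and "Study Day = Date – Reference Start Date". SAP section 10, which records departures from the protocol analyses, has one entry: "The patient-centered exploratory endpoints are not specified in the study protocol and only described in Section 3.7 of this SAP". It does not mention the early/late cut-off.

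**The concern.** Two periods meant to divide follow-up should share no day and leave none out. The SAE periods share day 30, and neither document has a tie rule for an event starting then. A programmer must either code the overlap and count such an event twice, or depart from the written SAP without a record.

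The mismatch with the AE rule is a second problem. A day-30 SAE would be early in the AE summary, but both early and late in the SAE summary. The two summaries would then not reconcile, although every SAE is also an AE.

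**Working it through.** The plan states no figure to reproduce here, so the check is of the rules themselves.

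**Inputs**
- AE rule (SAP 9.2) and protocol rule (Protocol 12.5): early if day ≤ 30, late if day > 30.
- SAE rule (SAP 9.2): early if day ≤ 30, late if day ≥ 30.
- Study day is the event date minus the index procedure date, a whole number with the procedure on day 0 (SAP 5.1).
- Enrolment is up to 200 patients (SAP 2.3).

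**Step 1: overlap and gaps.** Each rule was applied to every study day from 0 to 1870, the end of the five-year visit window (5 × 365 + 45 = 1870).

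| Rule | Days in both periods | Days in neither |
|---|---|---|
| AE rule and protocol rule | 0 | 0 |
| SAE rule as written | 1 (day 30) | 0 |
| SAE rule with late > 30 | 0 | 0 |

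**Step 2: event counts.** Let *e* be the SAEs before day 30, *a* those on day 30 and *b* those after it. As written, early = *e* + *a* and late = *a* + *b*. Their sum is *e* + 2*a* + *b*, against a total of *e* + *a* + *b*. The excess is *a*, so it is zero unless an SAE starts on day 30. The early count is the same under either rule.

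For illustration, assume six SAEs with onset on days 5, 29, 30, 30, 31 and 200:
- As written: early 4, late 4, sum 8.
- With late > 30: early 4, late 2, sum 6, which equals the total.

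**Step 3: SAEs against AEs.** Let *c* be the non-serious AEs after day 30. Late AEs number *b* + *c*, and late SAEs as written number *a* + *b*. Once *a* is at least 1, some late SAEs are not late AEs. The late-SAE count exceeds the late-AE count only if *a* > *c*.

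**Step 4: patient percentages.** A patient enters the late-SAE column wrongly only if the day-30 SAE is the only SAE that patient has on or after day 30. Someone with a later SAE is already in the column. With a denominator of 200, each wrongly added patient contributes 1/200 = 0.5 percentage points. For an assumed 0 to 3 such patients the inflation is 0 to 3 × 0.5 = 1.5 points. Neither document says how many to expect.

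**The case against.** The strongest reply is that this is an obvious slip with an obvious meaning. The SAE sentence presents itself as a repeat of the AE split, the protocol has one cut-off for all adverse events, and section 10 declares no change. All of that stands, and it shows which rule was intended. It does not remove the defect, because the SAP is the instruction from which the tables are programmed.

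A second reply is that the point rests on one sign in text read from a PDF. A misreading cannot be excluded. It is unlikely, because the strict sign was read as such one sentence earlier, but the original page should be checked.

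A reader might infer more than the documents support:

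- **Early plus late would always exceed the total.** This needs at least one SAE on day 30, and it identifies the defect only in event counts. In patient counts, someone with one SAE early and another late belongs in both columns even under the corrected rule.
- **The table would show more late SAEs than late AEs.** By Step 3, day-30 SAEs would have to outnumber all non-serious AEs after day 30. With three day-30 SAEs, that means at most two late non-serious AEs among up to 200 patients over up to five years, which is very unlikely.
- **Every patient with a day-30 SAE adds 0.5 points.** That is false for anyone with a later SAE. The figure also depends on the denominator. SAP 6.1 bases event rates on patients who had the event or were followed to the end of the visit window. If that number is *n* rather than 200, the step is about 1/*n*.
- **SAEs will cluster on day 30 because the first follow-up visit is then.** The split is by onset, not by visit date, and the visit has a window of ± 7 days (Protocol Table 13). SAP 6.2 imputes partial onset dates to the earliest possible date on or after the procedure, not to the visit. Nothing in the documents points to clustering.

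**Conclusion.** The late SAE category in SAP 9.2 is wrong as written. It overlaps the early category on one day and conflicts with the AE rule beside it and with Protocol 12.5, without a declared change. Followed literally, it inflates the late SAE event count by the number of SAEs starting on day 30. It inflates the late-SAE patient percentage by 0.5 points, at a denominator of 200, for each patient whose only SAE on or after day 30 starts on that day. If no SAE starts on day 30, nothing changes.

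The reach is narrow. The summary is descriptive. The 30-day MAE endpoint is defined and analysed separately (SAP 3.1 and 8.1) and does not use this split. Listings of all AEs and SAEs are also planned, so the numbers could be reconstructed. The conclusion assumes that the printed page carries the same sign as the text read here. This is an editorial correction of low severity, worth making before the tables are programmed.

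**What to change.** Check the sign for late SAEs in SAP 9.2 on the original page. If it includes day 30, change it to strictly more than 30 days, so that the SAE split matches the AE split in the same paragraph and Protocol 12.5. The early category stays as it is.

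The cost is one character in the SAP. No new data, protocol amendment or entry in section 10 is needed, because the change restores the protocol's own rule.
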